**Tertiary analyses for Aim 2.** Finally, we will measure whether, relative to the COM, patients in the DTM arm: **1) Experience less inpatient utilization** defined by *i. Hospitalization* (Y/N): whether each patient had at least 1 inpatient hospitalization; *ii. The number of hospitalizations* experienced by the patient; and *iii. Cumulative length-of-stay (inpatient days)* for each patient over the study period. **2) Experience less unscheduled T2D sick visits/days**, defined as **i.** Whether a subject has at least 1 unscheduled T2D sick clinic visit; and **ii.** Number of T2D unscheduled sick visits. **iii.** T2D sick days will be assessed monthly through self-report. Utilization outcomes (1-2) will be analyzed using Poisson regression to compare group rates. Despite discreteness of many of the scales cited above, the relatively large proposed sample size (100 per group), higher than what is necessary to detect differences, allows for the use of ANCOVA. All measures have documented validity evidence. Subgroup analysis will be exploratory, as no existing literature would support a particular effect size hypothesis. There are no plans for interim analyses or early stopping of the trial. Data

transformations will be considered for all analyses. Subgroup analyses are outlined separately below. **Assess data source adequacy.** Given the RCT approach, it is unlikely that demographics will be misrepresented in treatment groups. Thus, confounding is highly unlikely. However, demographic variables such as age, race/ethnicity, and insurance will be easy to measure through self-report, based on the success of an ongoing PCORI trial of telehealth-delivered CHF management (PI: [name]). These data will be a combination of self-report/medical record verification. The primary endpoint, HbA1c, is highly reliable as it is derived from a reputable, licensed laboratory. **Planned sensitivity analyses to determine the impact of key assumptions.** For all analyses, underlying assumptions will be evaluated using SAS diagnostic tools (PROC GENMOD, PROC MIXED, and PROC GLM). **Address missing data.** The best protection against missing data is to prevent it in the first place. To this end: 1) we have already partnered with the clinic directors to ensure that patient records will be available; 2) two separate team members, [name] and [name], will track the completion of data weekly (checking each other's data), which will be reported at weekly research meetings; and 3) each team member will have clearly defined tasks and will regularly report on progress. **Prevention and monitoring of missing data on outcomes:** Participants in both arms will be contacted (DTM through video visit; COM monthly by phone). This will be a "check-in" contact to assess how patients are doing and whether they have interacted with the healthcare system (i.e., ED visits). The RN will make all patient contact. If a patient does not continue with the study, we will ask for the reason for discontinuance. We will ask permission to collect outcome data as scheduled. We believe that this will help obtain outcome data in the spirit of ITT. In addition, we will use our pilot study and focus groups or structured interviews to identify potential challenges to data collection that we can address a priori. During data collection researchers Dr (s) [name] and [name] will assess weekly capture of all outcomes. The database management system, managed by the Biostatistics Unit, includes features that report test and form completion. The study team will monitor data collection and troubleshoot during regular meetings. We will also minimize risk of incomplete data by making surveys as easy as possible for the patient, conducted in their home; we will also perform cognitive pretesting with our PAC and field test surveys with pilot patients. **Statistical methods to handle missing data.** We will use standard methods of multiple imputation. Since HbA1c will be measured 4 times (baseline, 3 months 6 months and 12 months) pre-HbA1c data will necessarily be available and 3 or 6-month data (theoretically) will not. Therefore, a monotone missing data structure will be used. The missing data mechanism will be assumed to be missing at random (MAR). Similar approaches will be used for secondary outcomes-continuous and binary. **Recording and reporting reasons for dropout and missing data, and account for all patients in reports.** We will use the CONSORT diagram method to describe/account for subjects who drop out or for whom outcome variables are missing. Tables will reflect frequency/reasons for missing data. **Sensitivity of inferences to missing data methods and assumptions, and incorporation into interpretation.** A commonly used sensitivity analysis for the MAR assumption in multiple imputation is based on the pattern mixture model approach, modeling distribution of responses as a mixture of observed responses and missing responses. **Goals of planned HTE analyses.** We will evaluate whether the treatment effect in H/L patients with a caregiver participating differs from those that do not by examining the treatment x caregiver status interaction term. Similarly, we will also evaluate whether the treatment effect in female H/L patients differs from male patients by examining the treatment x gender interaction term. It should be emphasized, however, given our resources, there may be insufficient power to detect such interactions. Therefore, these analyses will be exploratory. If feasible, we will also evaluate the treatment x SE interaction. **HTE analysis plan.** In keeping with ICH E9 statistical principles for clinical trials (V.7G), the interaction terms for treatment x caregiver status, and treatment x gender will be included in the primary analysis, as well as main effects for treatment, caregiver, and gender. We plan on exploratory subgroup analyses to explore differential effects of treatment on caregiver

and gender groups. Upon finding a significant treatment x caregiver interaction (or treatment x gender interaction), the effect of treatment on A1C will be estimated separately for caregiver status (Y/N) (likewise for gender). Estimate of treatment effects and their 95% CI will be constructed. **The basis for all HTE claims based on appropriate statistical contrasts among groups being compared.** The literature and discussions with our CAB indicate the importance of family in the H/L culture. Given the different social/familial roles of women, we will also explore potential gender differences. We will also look at type of caregiver (paid/family) and explore caregiver type in a post hoc analysis to better understand the effect of caregiving. **HTE analysis plan to report all pre-specified analyses and, at minimum, the number of post-hoc analyses, including all subgroups and outcomes analyzed.** With the rich data set expected from this study, we will examine data patterns in an exploratory post-hoc way to identify potential trends not specified a priori. While we will use both exploratory and standard statistical approaches, p values, and associated CIs will be interpreted cautiously, as firm conclusions cannot be drawn. Post-hoc analyses will be adjusted for multiple testing. **Reporting plan to allow for assessments of the study's internal and external validity.** We will report trial results according to the CONSORT guidelines for reporting of RCTs, using the CONSORT 2010 checklist. We will report the progression of patients through the study using the CONSORT flow diagram, showing numbers of patients at each study point (enrollment, allocation, follow-up), and reasons for attrition at each point. For reporting qualitative results, we will use the COREQ a 32-item checklist for interviews/focus groups.

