## 6. RECRUITMENT METHODS

- *Describe the source of potential subjects*
- *Describe the methods that will be used to identify potential subjects*
- *Describe any materials that will be used to recruit subjects. A copy of any advertisements (flyers, radio scripts, etc.) should be submitted along with the protocol.*
- *If monetary compensation is to be offered, this should be indicated in the protocol*

To limit selection bias, and ensure true random selection, our Biostatistics Unit will randomly (using a random number generator) sample 400 patients from the 4,092 total patients.

**Recruitment:** The bilingual study RN, Multisite Patient Engagement Specialist or study coordinator will be responsible for recruitment at the various study sites. Given COVID-19 pandemic we will also be calling be patient over the phone to recruitment.

**Recruitment for Data Collection:** Eligible patients will be approached and called for consent (consent form 1) to have longitudinal data collected, including surveys at specified time points over the 12 months of their participation. Patients who are called will be give verbal consent. Next, bilingual study RN, Multisite Patient Engagement Specialist or study coordinator will obtain the randomization number from the Biostatistics Unit for the patient to determine if they were allocated to the DTM arm or COM arm. If the patient is randomized into the DTM arm, the recruiter will approach to obtain a second consent (consent form 2) to receive DTM. Verbal consent will be given for patients who are called for recruitment.

Informed consent will include a detailed but simple description, in patient's preferred language, of study risks/benefits.

**Recruitment for DTM:** Eligible patients will be approached or called for consent (consent 1) to have longitudinal data collected, including surveys at specified time

points over the 12 months from signing consent, in order to determine health outcomes. Next, the research coordinator will obtain the randomization number for the patient to determine if they were allocated to the DTM arm or COM arm. If the patient is randomized into the DTM arm, the coordinator will approach to obtain a second consent (consent 2) to receive DTM.

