Informed consent for DTM will include a detailed description, in English and Spanish, of the risks and benefits of the study with user-friendly images of the equipment. If the patients decline to participate in DTM, they will continue to receive standard of care and still have surveys administered and data collected over time (as agreed to in consent 1). Based on intention to treat (ITT), they nevertheless will be analyzed as part of the DTM group.

For those patients randomized to DTM, the RN will explain to the patients that if they agree to participate, they will be asked to measure vital signs daily, receive weekly telehealth “visits” with the telehealth RN (with appropriate assurances regarding confidentiality), and receive reminders of their weekly visits. The experienced bilingual RN will be trained in the proper recruitment of patients to eliminate selection bias based on a standardized protocol. The research RN will also explain to the DTM patient that s/he will have a bilingual trainer meet them at their home and that they will receive training on how to properly use the equipment.

For those patients randomized to COM, the research RN will have monthly phone contacts to determine how the patient is doing, how many days during the week they have been sick, and whether they have been to an unscheduled doctors visit, the ED or hospital during the last month and how many days they have been sick. Lastly, in both groups, the enroller will let patients know that they will be asked to complete pre and post surveys. The enroller will be trained on the proposed enrollment practices to ensure objective, unbiased and systematic selection and recruitment of participants.

DTM patients will be asked if they prefer to involve their caregiver; if patients agree, caregivers will be provided with the caregiver app (Figure 3). The bilingual enroller will explain to DTM patients that they will provide DTM training at their home.

We propose to study H/L patients with T2D, recruited from the Ambulatory Care Unit at LIJMC and the Division of General Internal Medicine Practice located in Queens NY, one of the most diverse populations in the world. We also propose to recruit at Southside Hospital. NUMC and Glen Cove Hospital as well as the Dolan Family Health Center. We selected these sites because 1) clinic patient statistics meet our enrollment criteria, with 4,092 adults H/L patients with T2D (well over the

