200 recruitment number required). 2) clinicians at these sites express enthusiasm for/commitment to the study and what it might mean for their H/L patients with T2D. These sites provide a real-world setting for implementation because LIJMC is where our target population of H/L disparity patients with T2D (many with limited English proficiency) receive their care (H/Ls comprise 27.5% of Queens' population).

Due to COVID-19 pandemic, we are also requesting patients be enrolled into the study via telephone by providing us with verbal consent. Surveys and questionnaires will be performed over the phone in the preferred language of the participant.

For patients reaching 6 month or 12 month follow-up during this time, interviews and surveys/questionnaires will also be collected over the phone.

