Health Literacy	Validation of Self-Reported Health Literacy Questions Among Diverse English and Spanish-Speaking Populations	Health literacy	The "confident with forms" question performed best for detecting inadequate (C-index = 0.82, (0.77-0.87)) and inadequate plus marginal HL (C index = 0.81, (0.76-0.86)); $p < 0.01$ for differences from other	Of 296 participants, 48% were Spanish-speaking; 9% were White, non-Hispanic; 47% had inadequate HL and 12% had marginal HL.

			questions), and performed comparably to the summative scale. The “confident with forms” question and scale also performed best across language, race/ethnicity, educational attainment, and age	
Weight	Weight scale	Bluetooth enabled weight	N/A	N/A
Blood Pressure	Blood pressure cuff	Bluetooth enabled BP cuff	N/A	N/A
Lipid Profile	Laboratory testing	LDL, HDL, total cholesterol	N/A	Standard laboratory test
Inpatient utilization	Chart review and weekly/monthly phone calls	Hospitalization (Y/N); number of hospitalizations; cumulative length-of-stay	N/A	Patient-reported (with EHR review verification)
Unscheduled T2D sick visits and number of sick days n	Weekly video visits (DTM) and monthly phone calls (COM)	Patient $\leq 1$ unscheduled sick visit; # of unscheduled T2D sick visits and days sick.	N/A	Patient-reported

\* The study team will inform the Labfly members to have proper precautions when they coming to subjects' home to do the lab work.

**1aiv. Exit qualitative interviews.** Patients and caregivers in the DTM arm who complete the 6-month intervention or drop out of the CER RCT study will be asked to provide feedback on their experiences. Through semi-structured phone interviews conducted by experienced qualitative researchers and recruitment specialists (in English and Spanish), we will assess patient/caregiver perceptions regarding intervention usefulness, feasibility/usability and identify particularly essential components.

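### No self-reported outcome is assigned to staff unaware of the arm, and sick visits and sick days in DTM are collected inside the treatment video visit

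*Combined protocol and SAP*

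**What the plan says.** **Check-in contacts.** Section 12, under prevention and monitoring of missing data, says: "Participants in both arms will be contacted (DTM through video visit; COM monthly by phone"). The stated aim is to "assess how patients are doing and whether they have interacted with the healthcare system (i.e., ED visits"). The next sentence is "The RN will make all patient contact".

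**Event outcomes.** Table 2 in Section 12 gives the source of unscheduled T2D sick visits and sick days as "Weekly video visits (DTM) and monthly phone calls (COM"). They are listed as patient-reported with no verification, whereas inpatient utilization, also patient-reported, is verified by EHR review.

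**COM contacts.** Section 6 says: "For those patients randomized to COM, the research RN will have monthly phone contacts to determine how the patient is doing". Section 11 adds that these calls are made to collect data.

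**DTM contacts.** Section 6 describes weekly telehealth visits with a telehealth RN. Section 11 lists the weekly visit as an intervention component and gives the DTM nurse a treating role alongside the physician. It also names encouragement by the RN as a route to higher self-efficacy. Section 12 sets a maximum of 24 visits over 6 months.

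**Scales.** Table 1 schedules them at months 1 and 6 in both arms. Under the COVID-19 provisions of Section 6, "Surveys and questionnaires will be performed over the phone in the preferred language of the participant". Section 11 likewise has secondary outcomes collected by phone in both groups. Neither names the caller.

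**Recruiters.** In Section 6 the "bilingual study RN, Multisite Patient Engagement Specialist or study coordinator will be responsible for recruitment at the various study sites". The same roles obtain the randomization number and seek the second consent from DTM patients.

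**The concern.** A patient's answer about confidence, mood, adherence or sick days can depend on who asks. In DTM, the sick-visit and sick-day questions are put during the contact that delivers the treatment, by a nurse the patient may have met up to 24 times. In COM they are put in a monthly data-collection call. The route of contact alone reveals the arm to whoever asks.

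If the month-6 scales are taken in the same way, a DTM patient has a plausible reason to answer favourably to someone involved in their care. A COM patient, who also speaks to a nurse each month, has less of one. The self-efficacy scale is especially exposed, because encouragement by the RN is part of how the intervention is meant to work.

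This would be differential measurement error. Randomization, analysis by intention to treat and ANCOVA adjustment do not remove it. The sensitivity analyses in Section 12 address model assumptions and missing data, not measurement. At stake is the interpretation of several patient-centered outcomes named in Aim 2.

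**Working it through.** The plan states no figure to reproduce on this point. The check is a reading of who collects what, followed by an illustration of scale.

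**1. Who collects each kind of outcome**

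| Outcome | Source in the plan | Collector named? | Exposed? |
|---|---|---|---|
| HbA1c, lipids | Laboratory (Table 2) | Not relevant | No |
| Finger-stick counts, weight, BP | Meter or device (Section 12) | Not relevant | No |
| Inpatient utilization | Patient report, EHR-verified (Table 2) | Weekly/monthly calls | Largely protected |
| Sick visits, sick days | Video visit (DTM), phone call (COM), unverified (Table 2) | Yes, by contact type | Yes, directly |
| ARMS-D, self-efficacy, distress, PAID, QoL | Self-report, by phone under COVID-19 | No | Possibly, by inference |

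Hypoglycemia is mixed (finger stick or reported symptoms) and is not counted below.

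**2. Share of the secondary list.** Section 12 numbers ten secondary outcomes, with adherence legible as two parts, so 11 items. Four are legibly self-report scales: ARMS-D, self-efficacy, distress and PAID. The fifth outcome is not legible in the text available; if it is a scale, the count is five.

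**3. Intensity of contact.** Up to 24 DTM visits against about 6 monthly COM calls over 6 months: 24 / 6 = 4 to 1. Table 1 has sick visits and sick days collected weekly in DTM and monthly in COM, while the tertiary analysis text says sick days are assessed monthly. Recall periods therefore differ by arm, and the direction of any resulting difference in capture cannot be told from the documents.

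**4. Illustration for a continuous scale.** Input from the sample size section: n = 112 per arm. Assumed: no true effect, and a reporting shift of b SD in DTM only.

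SE = √(2/112) = 0.1336

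P(reject) = Φ(b/SE − 1.96) + Φ(−b/SE − 1.96)

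| b (assumed) | b/SE | P(reject), normal | P(reject), t-test |
|---|---|---|---|
| 0 | 0 | 5.0% | 5.0% |
| 0.10 | 0.748 | 11.6% | 11.6% |
| 0.15 | 1.122 | 20.2% | 20.1% |
| 0.20 | 1.497 | 32.2% | 32.0% |

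At 100 per arm, the size given elsewhere in the plan, the t-test rates for 0.10, 0.15 and 0.20 SD are 10.8%, 18.4% and 29.1%. A shift of 0.20 SD is half the 0.4 SD effect quoted for secondary variables (0.20 / 0.4 = 0.5). ARMS-D is to be analysed by logistic regression, so these rates apply to it only by analogy.

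**5. Illustration for a count.** Sick visits are to be analysed by Poisson regression. Assumed: equal true means λ per patient, full capture in one arm and a fraction c in the other, no overdispersion.

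SE(log rate ratio) = √(1/(112λ) + 1/(112λc))

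- λ = 0.5: c = 0.9 gives 8.4%; c = 0.8 gives 20.0%.
- λ = 1.0: c = 0.9 gives 12.0%; c = 0.8 gives 35.0%.

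These rates are the same whichever arm is under-captured.

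**The case against.** The strongest reply is that the sentence on RN contact belongs to a paragraph about retention check-ins and does not assign the questionnaires. That is right. A reader might infer that the plan has the RN administer every scale, but the documents do not say so. Section 24 links survey completion to recruiters' home visits, Section 12 speaks of surveys done in the home, and Section 12 gives exit interviews to qualitative researchers and recruitment specialists. Section 6 also separates the telehealth RN from the research RN. If the research RN or a recruiter takes the month-6 scales in both arms, the one-sided mechanism is much weaker.

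This does not close the gap. Recruiters also learn the allocation under Section 6, so on either reading no one unaware of the arm is assigned. The reply also does not reach sick visits and sick days, where collection in the video visit is explicit.

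Three further objections stand. Self-report scales are a minority of the secondary list. The assumed shifts have no source in the documents. And masking the caller leaves the patient's own knowledge of the treatment, so it can remove only part of any bias.

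**Conclusion.** The point holds with limits. For unscheduled sick visits and sick days, collection within the treating contact in one arm, unverified, is written into the plan. For the month-6 scales it is a possibility left open, because no administrator is named and the only general statement on contact points to the RN.

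A reader might go further and infer that most secondary outcomes, or the trial's main result, are biased. The documents do not support that: 4 to 5 of 11 secondary items are self-report scales, and the primary HbA1c is a laboratory measure. Nor do they show that a bias exists or how large it is. The 12% to 32% false-positive range holds only if DTM reporting is shifted by 0.1 to 0.2 SD with no true effect at 112 per arm. For the event counts, even the direction is unknown.

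This is a cheap improvement, not a flaw that threatens the primary analysis.

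**What to change.** Amend the contact paragraph and Table 2 in Section 12 as follows.

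- Name who administers each self-reported outcome.
- Have the month-6 and any later scales, and the sick-visit and sick-day questions, read from one fixed bilingual script by existing bilingual study staff who neither recruited that patient nor deliver DTM to that patient. Section 24 refers to two bilingual recruiters, so each could interview patients enrolled by the other.
- Where feasible, do not tell the interviewer the arm. This cannot be guaranteed, since recruiters handle allocations.
- Ask the sick-visit and sick-day questions on the same monthly recall schedule in both arms, and use the same mode of administration in both.
- Give the telehealth satisfaction form, which only DTM patients receive, last.
- Check sick visits against the EHR, as already planned for inpatient utilization.
- Reconcile the statement on RN contact with Sections 6 and 20, where other staff contact patients, and with the exit-interview text in Section 12.
- State as a limitation that patients are unblinded and that some reporting bias may remain.

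The script should not ask patients to conceal their arm, because Section 24 withholds the randomization procedure at the first consent. Patient self-completion in REDCap is not proposed: Section 14 mentions REDCap only for holding data, and mixed modes could differ by arm.

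The cost is a script, some rescheduling of calls among existing staff, and one added item in the EHR review.
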